## **Study Protocol for Comparison between NICOM-Cheetah and FloTrac-Vigileo for Cardiac Output Monitoring.**

Patients will be recruited in the Surgical Intensive Care Unit (SICU) upon admission.

### **Inclusion criteria:**

- Patients who are deemed to require cardiac output monitoring
- Patients 21 years old and above
- American Society of Anesthesiologist (ASA) physical status 1 to 4

### **Exclusion criteria:**

- Patients who are not on mechanical ventilation
- Patients who are not in sinus rhythm
- Patients with allergy to adhesive tapes

50 consecutive patients admitted to the surgical intensive care unit (SICU) who are deemed to require cardiac output monitoring by the treating intensivist will be studied.

- Once a patient has been recruited, he/she will have the FloTrac® connected to the arterial catheter and the NICOM Cheetah® electrodes placed on the skin across the anterior thoracic wall.
- The SICU team will inform the study investigator about the recruitment and the data collection form will be filled by the study investigator.
- Cardiac Index, CVP and MAP values will be automatically and continuously recorded by the NICOM Cheetah® and FloTrac® computer. Data will be collected on a 15 minute basis over a 10-hour period using the data collection form and transcribed to a spreadsheet for data analysis.
- All patients will be treated as per department protocols at the discretion of the treating intensivist and no additional intervention will be performed.

### **Statistical Analysis**

This is an observational study and sample size/power calculation is not required. The agreement of the primary outcome (Cardiac Index) between the NICOM Cheetah® and FloTrac® will be assessed with Bland Altman's test. A disagreement of more than 20 percent will be deemed significant.

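### The primary agreement analysis sets no unit of analysis for about 40 correlated Cardiac Index pairs per patient, so pooling, averaging and a repeated-measures version all remain open

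*Combined protocol and SAP*

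**What the plan says.** The data-collection steps, printed under the Exclusion criteria heading, set the sample as "50 consecutive patients admitted to the surgical intensive care unit (SICU"). For each patient, "Data will be collected on a 15 minute basis over a 10-hour period using the data collection form", and the readings are then "transcribed to a spreadsheet for data analysis". No reduction to one value per patient is described. Care continues as usual during the recording: "All patients will be treated as per department protocols at the discretion of the treating intensivist".

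The Statistical Analysis section gives the whole method for the primary outcome in one sentence, "The agreement of the primary outcome (Cardiac Index) between the NICOM Cheetah® and FloTrac® will be assessed with Bland Altman's test", followed by the criterion "A disagreement of more than 20 percent will be deemed significant". It names no unit of analysis, repeated-measures version, variance model or confidence interval. It also does not say whether the 20 percent applies to the mean difference, to the limits of agreement or to individual pairs.

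**The concern.** In its standard form, Bland-Altman analysis takes the SD of the differences and the precision of the bias and limits from one independent pair per patient. Here each patient supplies about 40 pairs, and differences from the same patient and the same two devices can be expected to be positively correlated. An analyst given this spreadsheet has three routes, and the plan neither chooses nor excludes any of them.

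- **Pool all pairs as if independent.** Any confidence interval then claims the precision of 2,000 independent pairs although there are only 50 patients.
- **Average within patient.** The limits then describe 10-hour means. They are narrower than the limits for the single reading that a clinician sees on the monitor.
- **Use a repeated-measures version.** This is the suitable route. It must allow the true Cardiac Index to change over the 10 hours, since treatment continues throughout.

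This is the only planned analysis of the primary outcome. The routes answer different questions, and the choice could be made after the results have been seen.

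**Working it through.** **Inputs from the documents.** 50 patients; one reading every 15 minutes for 10 hours; a 20 percent criterion. The plan declines a sample size calculation ("This is an observational study and sample size/power calculation is not required"), so there is no stated figure to reproduce.

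**Number of pairs.** 10 × 60 / 15 = 40 per patient (41 if time zero is also read). 50 × 40 = 2,000 in total (2,050 with 41).

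**Assumptions, not in the documents.** Complete and balanced data. ρ, the between-patient share of the variance of the differences, is 0.1, 0.3, 0.5 or 0.8. The lag-1 autocorrelation within patient, φ, is 0 or 0.8.

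**Formulas.**
- The correlation between readings i and j of one patient is ρ + (1 − ρ)φ^|i−j|. With φ = 0 the second term applies only when i = j.
- v = mean of all 40 × 40 entries of that matrix.
- Design effect for the bias = 40v.
- Coverage of the pooled 95% interval for the bias = 2Φ(1.96/√(design effect)) − 1.
- SD of patient means relative to the single-reading SD = √v.
- At zero bias, averaging brings the limits within 20 percent when the true single-reading half-width lies between 20 and 20/√v.

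**Worked example (ρ = 0.5, φ = 0).** v = 0.5 + 0.5/40 = 0.5125. The design effect is 40 × 0.5125 = 20.5, so 2,000 pairs carry the information of 2,000/20.5 ≈ 98 for the bias. The pooled standard error is too small by a factor of √20.5 = 4.5. Coverage is 2Φ(1.96/4.53) − 1 = 33%. The averaged limits are √0.5125 = 0.716 of the single-reading width, and the reversal window runs from 20 to 20/0.716 = 27.9 percent.

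**All settings.** The two columns marked * are simulated, with 20,000 trials per setting. The pooled interval for a limit uses SE = SD × √(1/N + 1.96²/(2(N − 1))) with N = 2,000. The last column gives how often |bias| + 1.96 × SD of patient means is at most 20 when the true single-reading half-width is 25 percent and the true bias is zero; it was run for ρ = 0.3, 0.5 and 0.8.

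| φ | ρ | Design effect | Pooled interval coverage, bias | Pooled interval coverage, limit* | Averaged/single width | Upper end of reversal window | Averaged limits within 20 percent* |
|---|---|---|---|---|---|---|---|
| 0 | 0.1 | 4.9 | 62% | 78% | 0.350 | 57.1 | – |
| 0 | 0.3 | 12.7 | 42% | 54% | 0.563 | 35.5 | 99.9% |
| 0 | 0.5 | 20.5 | 33% | 39% | 0.716 | 27.9 | 72.4% |
| 0 | 0.8 | 32.2 | 27% | 29% | 0.897 | 22.3 | 6.9% |
| 0.8 | 0.1 | 11.2 | 44% | 53% | 0.529 | 37.8 | – |
| 0.8 | 0.3 | 17.6 | 36% | 43% | 0.663 | 30.2 | 91.9% |
| 0.8 | 0.5 | 24.0 | 31% | 35% | 0.775 | 25.8 | 43.9% |
| 0.8 | 0.8 | 33.6 | 26% | 27% | 0.917 | 21.8 | 4.6% |

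**Point limits.** The mean pooled SD is 0.988 to 0.999 of the true single-reading SD, so pooling barely moves the limits themselves. In the 25 percent example, pooled limits and limits from one-way ANOVA variance components fall within 20 percent in 0.2% of trials or fewer in every setting.

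**The case against.** The strongest reply is that the harm attaches to things the plan does not contain.

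- **No confidence interval is planned.** On point estimates with balanced data, pooling and the repeated-measures method give practically the same limits. This stands: the coverage figures matter only if intervals are reported.
- **No averaging is mentioned.** The reversal needs averaging, a 20 percent criterion read against the limits, a low or moderate ρ, and a true half-width not far above 20 percent. This also stands. If the 20 percent refers to the mean difference, pooling and averaging give the same point value with balanced data and no reversal is possible. At ρ = 0.8 the effect is small.
- **The text is silent rather than wrong.** Repeated-measures versions also carry the Bland-Altman name, and agreement of 10-hour means is a legitimate target if labelled as such. True, but a plan for the only primary analysis should say which is meant.
- **Unequal numbers of readings per patient were not examined.** Correct. They would weight patients unequally under pooling, and the figures above do not extend to that case.

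These points limit the size of the harm but do not close the gap. Observational status is the plan's reason for omitting a sample size; it is no reason to leave the primary analysis open to routes with different answers.

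**Conclusion.** The concern holds as an omission that should be fixed. About 40 dependent pairs per patient go to a method whose standard form assumes independence, and nothing in the document settles how they are handled. The count of pairs is certain, and the direction of both effects follows from positive correlation within patients. Their size rests on assumed ρ and φ, since the document gives neither.

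For pooling, the damage is confined to confidence intervals, if any are reported. For averaging, it falls on the limits and on any conclusion drawn from them: large at low ρ, small at high ρ, and absent if the 20 percent refers to the mean difference.

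**What to change.** In the Statistical Analysis section, state the following:

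1. The method is Bland-Altman for repeated measures with a varying true value, and the patient is the unit of independence.
2. Limits for single readings are bias ± 1.96 × √(between-patient variance + within-patient variance), with the components taken from a mixed model with a random patient effect or from one-way ANOVA.
3. 95% confidence intervals are reported for the bias and both limits by a method that respects clustering, such as resampling whole patients.
4. The 20 percent criterion is judged on single-reading and not patient-averaged differences, and the quantity it is compared with is named.

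The cost is a few sentences and slightly more analysis code, with no extra patients or data. The intervals will be wider than pooled ones and the limits wider than averaged ones; with balanced data the point limits will hardly differ from pooled ones. With 50 patients, patient-resampling intervals are slightly optimistic: simulated coverage was 93-95% for the bias and 91-94% for the limits (1,500 trials, 600 resamples each).
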